11.4.3.2. Secondary Efficacy Analysis

Intent-to-Treat Estimand

The intent-to-treat estimand used for the key secondary efficacy analyses is the treatment policy strategy, specifically:

- A. The patient population is defined as the ITT population (Section 11.3.1.1).
- B. The key secondary efficacy endpoints are defined in Section 4.2.1.
- C. The intercurrent events of interest are the administration of study treatment and the administration of subsequent therapies. The interruption of study treatment and the change in subsequent therapies are ignored, and the value for the key secondary efficacy endpoint is used regardless of adherence to study treatment and subsequent therapies.
- D. For the percent change in fasting TGs, the analysis method of robust regression for a non-normal distribution will yield the population-level summary for each treatment group

of mean with associated standard error (SE), and the mean difference between the treatment groups will be provided with the SE, 95% CI, and p value.

For the percent change in ApoC3, the analysis method of mixed-effect model with repeated measures (MMRM) approach for a normal distribution will yield the population-level summary for each treatment group of mean with associated SE, and the mean difference between the treatment groups will be provided with the SE, 95% CI and p value.

Statistical Analysis

For the key secondary efficacy endpoints (defined in Section 4.2.1) and other secondary efficacy endpoints (described in Section 4.2.2) collected in the DBTP, descriptive summaries and analyses will be performed in the ITT population, using values obtained regardless of adherence to study treatment and subsequent therapies (ITT estimands).

For descriptive summaries, percent change, and when appropriate change from baseline, in TC, TG, calculated non-HDL-C, ApoC3, ApoB48, and ApoB100, will be provided at each time point. All measurements, scheduled or unscheduled, will be assigned to analysis windows defined in the SAP in order to provide an assessment for these time points. Laboratory assessments other than the ones provided by the central laboratory will be excluded. For TG, measurements on non-fasting patients will be excluded. The time profile of each parameter will be plotted by treatment group with the corresponding SEs.

Multiple types of measurements are planned to be analyzed during differing time points in the trial, specifically continuous measurements expected to have a normal distribution (example: percent change in TC), continuous measurements expected to have a non-normal distribution (example: TG), and binary measurements.

I. Continuous endpoints anticipated to have a normal distribution

Continuous secondary variables anticipated to have a normal distribution (ie, lipids other than TG) will be analyzed in the ITT population at week 52 using an MMRM approach. Specifically, the model will contain fixed categorical effects of treatment group, planned time points up to the time point of interest, and treatment-by-time point interaction, as well as the continuous fixed covariates of corresponding baseline value and baseline value-by-time point interaction. This model will be run using Statistical Analysis Software (SAS) mixed procedure with an unstructured correlation matrix to model the within-patient errors.

II. Continuous endpoints anticipated to have a non-normal distribution

Continuous secondary efficacy endpoints anticipated to have a non-normal distribution (ie, TG), will be analyzed in the ITT population at week 52 using a robust regression model (ie, ROBUSTREG SAS procedure with M-estimation option) with treatment group as main effect and corresponding baseline value(s) as a covariate. Missing values will be addressed using a multiple imputation approach, which will be described in the SAP. The variables in the multiple imputation model will at least include the same variables as used in the robust regression model. The treatment group combined means will be provided with respective SE estimates. The combined mean difference between the treatment groups will be provided with the SE, 95% CI, and p value.

III. Binary endpoints

Binary secondary efficacy endpoints will be analyzed using logistic regression with treatment group as main effect and corresponding baseline value(s) as a covariate. Missing values will be addressed using a multiple imputation approach, which will be described in the SAP. The variables in the multiple imputation model will at least include the same variables as used in the logistic regression model. Treatment effects will be compared, and the combined odds ratio estimate between the treatment groups with their corresponding 95% CI and p value will be provided.

11.4.4. Control of Multiplicity

Interim Analysis

An interim analysis is planned when approximately 50% (N=60) of patients have completed the DBTP. This will consist of the final data contributing to the analysis of the applicable variables up to the week-52 visit for these patients. A small alpha adjustment of 0.001 has been made to account for this treatment-unblinded interim, since the sponsor does not plan to stop the study early for evinacumab treatment benefit – efficacy analyses will be descriptive in nature. The purpose of this interim analysis is administrative, specifically to aid in the planning of future studies. Therefore, the significance level for the final efficacy analysis at the first-step analysis will be 0.049.

First-Step Analysis

The first step analysis will be conducted when all patients have been randomized and all data through week 52 (DBTP) has been collected and validated. In order to address multiple key secondary efficacy endpoints (eg, percent change ApoC3 from baseline to week 52, and percent change fasting TG from baseline to week 52) at the first-step analysis, the overall type-I error will be controlled by the use of a hierarchical inferential approach. Statistical significance of the primary parameter is required before drawing inferential conclusions about the first key secondary parameter at the 0.049 alpha level. Inferential conclusions about successive key secondary parameters require statistical significance of the prior parameter within the hierarchy. The hierarchy testing sequence is the order of endpoints as presented in Section 4.2.1 Key Secondary Efficacy Endpoints. This fixed hierarchical approach will ensure a strong control of the overall type-I error rate at the 0.049 level.

No further adjustments will be made for other secondary endpoints, for which p values will be provided for descriptive purposes only.

No adjustment will be made for the final (Section 11.5.3) statistical analyses, since the primary and key secondary efficacy endpoints will have been concluded at the time of the first step analysis.

11.4.5. Safety Analysis

Summaries of safety results will be presented by treatment group for patients in the SAF. No formal inferential testing will be performed. Summaries will be descriptive in nature.

All safety analyses will be performed using the following common rule:

- The baseline value is defined as the last available value before the first dose of double-blind study treatment.

11.4.5.1. Adverse Events

All AEs reported in this study will be coded using the currently available version of the Medical Dictionary for Regulatory Activities (MedDRA®). The verbatim text, the preferred term (PT), and the system organ class (SOC) will be provided in patient listings.

Definitions

For safety variables, the following observation periods are defined:

- The pre-treatment period is defined from the day the ICF is signed to the day before the first dose of double-blind study treatment.
- The TEAE observation period is defined from the day of the first dose of double-blind study treatment to the day of the last dose of double-blind study treatment + 168 days (24 weeks) (residual effect of treatment for IV dose regimen is expected until 24 weeks after the last dose of study drug).

The post-treatment observation period is defined as the time from the day after the end of the TEAE period to the last study visit.

Treatment-emergent adverse events are defined as those adverse events that developed, worsened, or became serious during the TEAE period.

Analysis

Adverse event incidence tables will present data by SOC sorted alphabetically and PT sorted by decreasing frequency, and summarize the number (n) and percentage (%) of patients experiencing an AE. Multiple occurrences of the same event in the same patient will be counted only once in the tables. Data conventions for missing or partial AE dates will be addressed in the SAP. The denominator for computation of percentages is the SAF population within each treatment group.

Summaries of TEAE incidences will include:

- All TEAEs
- All treatment-emergent SAEs, including patient deaths
- All treatment-emergent AESIs
- TEAEs by severity (according to the grading scale outlined in Section 10.2.5), depicting the worse TEAE severity for those patients with multiple occurrences of the same event
- All TEAEs leading to permanent treatment discontinuation

An AE patient listing will be provided for all patient deaths occurring during the TEAE period and the post-treatment period.

11.4.5.2. Other Safety

Definitions

The following definitions will be applied to laboratory parameters and vital signs:

- The potentially clinically significant value (PCSV) criteria are defined as abnormal values considered medically important by the sponsor according to predefined criteria/thresholds based on literature review and defined by the sponsor for clinical laboratory tests and vital signs. Potentially clinically significant value criteria will be provided in the SAP.
- PCSV criteria will determine which patients had at least 1 PCSV during the TEAE period, taking into account all evaluations performed including unscheduled or repeated evaluations. The number of all such patients will be the numerator for the PCSV percentage.
- The treatment period used for the quantitative analysis of laboratory and vital sign data is defined from the day after the first dose of double blind study treatment to the day of the last dose of double-blind study treatment + 28 days.

Analysis

Summary statistics of all laboratory variables (including lipid HDL-C) and all vital sign parameters (raw data and changes from baseline) will be calculated for each protocol-scheduled visit assessed during the respective treatment periods. For selected parameters, mean changes from baseline with the corresponding SE may be plotted over time in each treatment group.

The incidence of PCSVs at any time during the respective TEAE periods will be summarized regardless of the baseline level, and again according to the following baseline categories:

- Normal/missing
- Abnormal according to PCSV criterion or criteria

For laboratory parameters for which a PCSV criterion is not defined, similar table(s) using the normal range will be provided, regardless of baseline level.

Listings will be provided with flags indicating the laboratory values meeting PCSV criteria.

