The screening period may last up to 28 days and consists of 1 visit. During the screening period, all patients will undergo the informed consent process and standard screening procedures. Laboratory assessments used to determine eligibility may be repeated once during the screening period. The fasting TG measurement can be repeated once for values >500 mg/dL but <880 mg/dL.

A mandatory sample for DNA isolation will be obtained for patients who do not have documentation of prior genetic testing in order to confirm the absence of FCS due to homozygous or compound heterozygous LoF mutations in *LPL*. For these patients, the results of the screening FCS genotyping confirming no homozygous or compound heterozygous LoF mutations in *LPL* must be available before the patient can be enrolled in the study.

Patients who have screen-failed are not eligible for rescreening, unless rescreening is discussed and agreed with the medical monitor.

After confirmation of eligibility, patients will proceed to visit 2 for randomization.

Double-Blind Treatment Period (Day 1 to Day 365)

Principal investigators, study site personnel, study patients, and the Regeneron study team will all be blinded to treatment during the DBTP.

Randomized patients will receive either evinacumab administered IV at a dose of 20 mg/kg IV or matching placebo Q4W (± 4 days) during the DBTP. On dosing days, all assessments and lab samples (including urine or serum pregnancy tests for WOCBP) should be performed before the dose of study drug is administered. All samples should be collected following at least an 8-hour fast. Medications are permitted to be taken with water as medically indicated. Electrocardiograms should be performed before blood is drawn. Additionally, vital signs should be measured, and AEs monitored pre-dose, at the end of study drug infusion, and at 30 minutes and 60 minutes post-end of infusion. Patients will be closely monitored for a minimum of 60 minutes after IV administration of evinacumab or matching placebo.

Efficacy and safety procedures, including a standard lipid panel, dietary and alcohol use review, and the completion of a pain questionnaire will be performed as outlined in the Schedule of Events ([Table 1](#)).

Serum samples for the determination of total evinacumab and total ANGPTL3 should be collected prior to AND at the end of infusion of study drug (within 30 minutes from the end of infusion).

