Study Procedure														
Electrocardiogram ⁸	X	X												
Adverse Events	X	X	X	X	X	X	X	X	X	X	X	X	X	X
Laboratory: ⁵														
Hematology	X	X												
Blood Chemistry	X	X	X	X		X		X		X		X		X
Pregnancy Test ^{9,10}	X	X	X	X	X	X	X	X	X	X	X	X	X	X
Pharmacokinetics and Immunogenicity Sampling:														
Drug Conc. Sample ¹¹		X	X	X	X	X	X	X	X	X	X	X	X	X
ADA and NAb sample ¹²		X				X				X				
Biomarkers:														
Biomarker		X							X					
Serum/Plasma ¹³														
Lipoprotein Analysis by NMR		X												
Optional Pharmacogenomics:														
DNA Sample (Optional) ¹⁴		X												
Other:														
Mandatory DNA Sample for FCS	X													
Genotyping for Subset of Patients ¹⁵														
Dietary Review	X	X	X	X	X	X	X	X	X	X	X	X	X	X
Alcohol Intake Review	X	X	X	X	X	X	X	X	X	X	X	X	X	X

Table 2: Schedule of Events for the Off-Drug Follow-up Period

	End of DBTP	Off Drug Follow-Up		
		V15	V16	End of Study V17
Visit # (V)	V15	V16		End of Study V17
Week	52	62		72
Day	365	435		505
Window (day)	±4	±7		±7
Efficacy:				
Lipid Profile ¹	X	X	X	
Special Lipids ¹	X		X	
Presence of Abdominal Pain (1-Item Question)	X	X	X	
HAP-Pain Questionnaire	X	X	X	
Safety:				
Concomitant Meds and Treatment	X	X	X	
Weight	X	X	X	
Vital Signs	X	X	X	
Physical Examination			X	
Electrocardiogram ²			X	
Adverse Events	X	X	X	
Laboratory : ³				
Hematology	X		X	
Blood Chemistry	X	X	X	
Pregnancy Test ^{4,5}	X		X	
Pharmacokinetics and Immunogenicity Sampling: ⁶				
Drug Conc. Sample	X		X	
ADA and NAb Sample	X		X	
Biomarkers:				
Biomarker Serum/Plasma	X		X	
Lipoprotein Analysis by NMR	X			
Other:				
Dietary Review	X	X	X	
Alcohol Intake Review	X	X	X	

9.1.1. Footnotes for the Schedule of Events Tables**9.1.1.1. Footnotes for Table 1 Schedule of Events (DBTP)**

1. Medical history should include detailed cardiovascular and pancreatitis history.
2. Height will be measured in meters (m). Body weight will be assessed using calibrated scales. Patients should void (empty bladder) prior to weight assessment. Patients should be wearing undergarments only and no shoes during weight assessments. Body weight will be recorded to the nearest 0.1 kg. Body mass index (BMI) is calculated as weight (kg)/height(m)².
3. Postmenopausal status will be confirmed by measurement of FSH.
4. At dosing visits, all assessments (including urine or serum pregnancy tests for WOCBP) should be performed before the dose of study drug is administered.

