11.3.1.2. Modified Intent-to-Treat

The modified ITT (mITT) population is defined as the all-randomized population who took at least 1 dose or part of a dose of study drug and includes patients for whom the primary endpoint is evaluated during the efficacy treatment period. The efficacy treatment period is defined as the time from the first double-blind study drug administration up to 35 days after the last double-blind study drug administration. Patients in the mITT population will be analyzed according to the treatment group allocated by randomization.

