### **5.8.3. Clinical Laboratory Measurements**

Clinical laboratory parameter actual values (quantitative) and change from baseline values will be descriptively summarized at baseline and each post-baseline visit for the study treatment period, by at least patient number, mean, median, Q1, Q3, SD, minimum and maximum.

Clinical laboratory parameters mean changes from baseline, with the corresponding SE, can be plotted at each visit in the case results warrant further investigation. These parameters will be presented by the biological functions defined in Section 4.8.2. For glucose, only fasting samples will be included in the summaries.

Individual patient laboratory parameter measurements will be additionally evaluated by PCSV criteria (See Appendix 10.3), specifically identifying patients with at least one post-baseline measurement that meets the PCSV criteria within the TEAE period. These laboratory parameters will be presented by the biological functions defined in Section 4.8.2. The incidence of PCSVs at any time during the TEAE period will be summarized regardless of the baseline level, and again according to the following baseline categories:

- Normal (according to PCSV criterion/criteria)/missing
- Abnormal according to PCSV criterion or criteria

Patient listings of laboratory measurements that meet PCSV criteria will be provided for the report appendix.

For those laboratory parameters that don't have an associated PCSV criteria, similar summary tables can be provided based on measurements outside the central laboratory normal ranges, if applicable.

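### The protocol's cut-off at last dose + 28 days drops a Week 52 laboratory or vital-sign visit made more than 28 days after the actual last dose, although the visit windows allow gaps of up to 36 days

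*Protocol*

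**What the plan says.** Protocol 11.4.5.2 (Other Safety) sets the period for quantitative laboratory and vital-sign data. It ends at "to the day of the last dose of double-blind study treatment + 28 days". Summary statistics for all laboratory variables and vital signs "will be calculated for each protocol-scheduled visit assessed during the respective treatment periods".

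The schedule around that end point is as follows.

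- **Dosing.** Protocol 6.1 gives evinacumab or "matching placebo Q4W (± 4 days) during the DBTP". In Protocol Table 1 the last dose is at Week 48, Day 337, ±4 days.
- **End of treatment.** Protocol 6.1 labels the period "Double-Blind Treatment Period (Day 1 to Day 365". The Week 52 visit stands in "Table 2: Schedule of Events for the Off-Drug Follow-up Period" at Day 365, ±4 days.
- **Hematology.** The Table 1 row reads "Hematology X X", with the two marks under screening and Day 1. Table 2 adds Week 52 and Week 72, with nothing at Week 62.

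Elsewhere the protocol uses a longer on-treatment margin. The efficacy treatment period in 11.3.1.2 runs "up to 35 days after the last double-blind study drug administration".

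SAP 5.8.3 summarizes laboratory values at "each post-baseline visit for the study treatment period", and SAP 5.8.4 does the same for vital signs. SAP 5.8 (general common rules) assigns all safety measurements to the Global Analysis Windows of SAP Table 1. SAP 1.2.4, which lists the departures from the protocol's statistical section, does not mention the + 28-day rule.

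**The concern.** The cut-off counts from the actual last dose and allows exactly one nominal dosing interval. It therefore lands on the nominal Week 52 day for a patient dosed on Day 337, and leaves no room for the windows on either date. A patient dosed on Day 337 and seen on Day 366 has followed the protocol, yet loses the Week 52 values from the quantitative summaries.

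Week 52 is the time point with the longest exposure. Chemistry and vital signs keep their earlier visits if it is lost. Hematology has no earlier scheduled post-baseline sample, so an excluded patient contributes no scheduled hematology change from baseline in the period. Whether a patient is counted would turn on a day or two of scheduling, which has nothing to do with treatment.

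**Working it through.** **Inputs.** Last dose: Week 48, ±4 days (Protocol 6.1 and Table 1). End-of-treatment visit: Week 52, ±4 days (Protocol Table 2). Cut-off: actual last dose + 28 days (Protocol 11.4.5.2). Efficacy margin for comparison: 35 days (Protocol 11.3.1.2).

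**Nominal days.** Day = 1 + 7 × week. Week 48 is 1 + 336 = Day 337 and Week 52 is 1 + 364 = Day 365, both as printed in the tables. 337 + 28 = 365, so the cut-off equals the nominal visit day.

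**Range of compliant gaps.** Dose days run from 333 to 341 and visit days from 361 to 369. The shortest gap is 361 − 341 = 20 days and the longest is 369 − 333 = 36 days.

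**Condition for exclusion.** Let d be the offset of the Week 48 dose and v the offset of the Week 52 visit, each an integer from −4 to +4. The gap is 28 + v − d. It exceeds 28 exactly when v > d.

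**Enumeration of the 9 × 9 = 81 date pairs.** Of these, 9 have v = d, and the remaining 72 split evenly, so v > d in 36.

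| End of period | In-window pairs cut |
|---|---|
| last dose + 28 days | 36 of 81 |
| last dose + 32 days | 10 of 81 |
| last dose + 35 days | 1 of 81 (dose Day 333, visit Day 369) |
| last dose + 36 days | 0 of 81 |

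**Which visits are cut at + 28 days.**

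- Late visits (v = 1 to 4): 5 + 6 + 7 + 8 = 26 of 36 pairs are cut and 10 are kept. For example, a dose on Day 341 moves the cut-off to Day 369, so a visit on Day 369 stays in.
- On-time or early visits (v = −4 to 0): 0 + 1 + 2 + 3 + 4 = 10 of 45 pairs are cut. For example, a dose on Day 333 moves the cut-off to Day 361, so an on-time visit on Day 365 is lost.

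**From pairs to patients.** This needs a distribution of visit timing, which the documents do not give. Three assumed cases:

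- Week 52 always booked exactly 28 days after the last dose: 0%.
- Independent uniform offsets over ±1 day: 3 of 9 pairs, 33%.
- Independent uniform offsets over ±4 days: 36/81 = 44%.

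None of these is an upper bound. If visits systematically ran a day or more beyond 28 days after the dose, the share would be higher.

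**SAP window.** For Week 52, K = 13 in SAP Table 1. The window runs from 15 + 28 × 12 = Day 351 to 42 + 28 × 12 = Day 378. Every compliant visit (Day 361 to 369) falls inside it.

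**The case against.** The strongest reply is that the SAP already solves this. SAP 5.8, 4.8.2 and 4.8.3 put laboratory and vital-sign data into the global windows, and SAP 6.4 applies those windows to all analyses. The SAP states no + 28-day end for these summaries, and the protocol leaves analysis windows to the SAP (11.6). Most of this stands: on the window rules alone, the values are kept. What remains is that SAP 5.8.3 and 5.8.4 refer to a study treatment period that the SAP does not define for these summaries, while SAP 1.2.4 lists no change to the protocol's rule. Two programmers could reasonably produce different Week 52 tables.

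A second reply is that little is at stake. The SAP (Section 1) records that the study was administratively discontinued for poor recruitment, and all remaining analyses are descriptive. The 35-day comparator belongs to the mITT analysis, which SAP 1.2.4 drops. This also stands and limits the weight of the point.

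Three stronger readings are tempting, and the documents do not support them.

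- *Every late Week 52 visit is lost.* The trigger is the gap from the actual dose. Some late visits are kept and some on-time or early ones are cut.
- *About 44% of full-course patients lose their Week 52 values.* That figure counts date pairs under assumed independent uniform timing. It is not an estimate of patients.
- *Abnormal Week 52 results go unseen.* PCSV incidence and the supporting listings use the treatment-emergent period, last dose + 168 days (Protocol 11.4.5.1 and 11.4.5.2; SAP 5.8.3), so the sample still counts there. Percent change in HDL-C to Week 52 is also a separate endpoint (Protocol 4.5), with no + 28-day limit stated there.

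**Conclusion.** The point holds for the protocol's stated rule. A Week 52 visit more than 28 days after the actual last dose is excluded from the quantitative by-visit summaries, although compliant gaps reach 36 days. The loss is confined to those summaries and matters most for hematology, where no other scheduled post-baseline sample exists before off-drug follow-up. Its size in date pairs is 36 of 81, falling to 1 of 81 at the 35-day margin used for efficacy and to none at 36 days. Its size in patients is unknown, because visit timing is not given. The conclusion concerns patients who receive the Week 48 dose and takes the protocol rule as written. The SAP's windows reduce the problem without clearly removing it. With the study stopped early and no inference planned, this is a worthwhile correction of small practical effect.

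**What to change.** **Protocol 11.4.5.2.** End the quantitative laboratory and vital-sign period at last dose + 36 days. Alternatively, state that the scheduled Week 52 visit is always included for patients given the Week 48 dose.

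**SAP 5.8.3 and 5.8.4.** Define the study treatment period by the Global Analysis Windows of SAP Table 1 through Week 52 (Day 378). This is safer than writing a last-dose cut-off into the SAP, which could remove values its windows now keep, such as Week 52 values from patients who missed the Week 48 dose. Note the departure from the protocol's + 28-day rule in SAP 1.2.4.

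**Cost.** A few sentences of text, with no new data collection and no change to patient care. Under the protocol change, values up to 36 − 28 = 8 days further from the last infusion would count as on-treatment. That is well within the 24 weeks (168 days) of residual effect that Protocol 11.4.5.1 assumes.
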